5.2.12. Adequate Post Baseline Tumor Assessment

An adequate assessment is defined as an assessment where a response of CR, PR, Stable Disease (SD), non-CR/non-PD, or PD has been provided by the investigator or ICR for the analyses by investigator or ICR respectively. Timepoints where the response is not evaluable or no assessment was performed will not be used for determining the censoring date.

5.2.13. Unscheduled Assessments

Unless otherwise specified, unscheduled assessments will not be displayed in summary tables by nominal visit/timepoint. Unscheduled assessments will be used when deriving baseline and worst case on-treatment for safety analyses. Additionally, unscheduled tumor assessments will be used for efficacy analyses (eg, defining date of progression/censoring, best overall response, date of last contact).

5.2.14. Standard Derivations and Reporting Conventions

The following conversion factors will be used to convert days into weeks, months or years:
1 week = 7 days, 1 month = 30.4375 days, 1 year = 365.25 days.

Percentages will be reported to one decimal place. The rounding will be performed to closest integer/first decimal using the common mid-point between the two consecutive values. Eg, 5.1 to 5.4 will be rounded to an integer of 5, and 5.5 to 5.9 will be rounded to an integer of 6.

5.2.15. Analyses for Continuous Data

Continuous variables will be summarized using descriptive statistics ie, number of non-missing values and number of missing values [ie, n (missing)], mean, median, standard deviation (SD), minimum, maximum and first and third quartile (Q1 and Q3). CCI [REDACTED] PK summaries will also include coefficient of variation percent (%CV).

In case the analysis refers only to certain visits, percentages will be based on the number of patients with an assessment at that visit, unless otherwise specified.

5.2.16. Analyses for Categorical Data

Qualitative variables will be summarized by frequency counts and percentages. Unless otherwise specified, the calculation of proportions will include the missing category. Therefore counts of missing observations will be included in the denominator and presented as a separate category.

In case the analysis refers only to certain visits, percentages will be based on the number of patients with an assessment at that visit, unless otherwise specified.

5.2.17. Analyses for Time to Event Data

Time to event endpoints will be summarized using the Kaplan-Meier method and estimated survival curves will be displayed graphically when appropriate. Graphs will describe the number of patients at risk over time. The median, first and third quartiles, and probabilities of an event at particular points in time will be estimated by the Kaplan-Meier method. Confidence intervals for medians and quartiles are based on the Brookmeyer-Crowley¹ method. Confidence intervals for the estimated probability of event at a particular timepoint will be generated using the log(-log) method with back transformation to a confidence interval on the untransformed scale. Summaries of the number and percentages of patients with an event will also be provided on summary tables and/or figures.

5.3. Methods to Manage Missing Data

Unless otherwise specified, all data will be evaluated as observed, and no imputation method for missing values will be used.

Any imputations will occur at the analysis dataset level. Additionally, in all patient data listings imputed values will be presented and flagged as imputed.

Missing statistics, eg, when they cannot be calculated, should be presented as 'ND' for not done, 'NR' for not reached or 'NA' for not applicable. For example, if N=1, the measure of variability cannot be computed and should be presented as 'ND' or 'NA'.

5.3.1. Missing Dates

For purposes of data listings, dates will reflect only the information provided by the investigator on the CRF.

If start dates for adverse events or concomitant medications are completely missing a worst case approach will be taken whereby the events will be considered treatment emergent and the medications will be considered concomitant. If only partial information are available (eg, only a month and year or only a year) and the partial information provide sufficient information to indicate the dates are prior to the start of study treatment (eg, month/year less than month/year of first dose) then these will be considered to have started prior to treatment; otherwise a similar worst case approach will apply and these will be considered to have started after treatment.

Date of Last Dose of Study Treatment

No imputation will be done for first dose date. Date of last dose of study treatment, if unknown or partially unknown, will be imputed as follows:

- If the last date of study treatment is completely missing and there is no End of Treatment (EOT) CRF page and no death date, the patient should be considered to be ongoing and use the data cutoff date for the analysis as the last dosing date; or
- If the last date of study treatment is completely or partially missing and there is EITHER an EOT CRF page OR a death date available (on or prior to the data cutoff date), then impute this date as the last dose date:

= 31DECYYYY, if only Year is available and Year < Year of min (EOT date, death date),

= Last day of the month, if both Year and Month are available and Year = Year of min (EOT date, death date) and Month < the month of min (EOT date, death date), or

= min (EOT date, death date), for all other cases.

Missing or Partial Death Dates

Missing or partial death dates will be imputed based on the last contact date:

- If the entire date is missing it will be imputed as the day after the date of last contact (see derivation of date of last contact in [Section 5.2.7](#)); or

If the day or month is missing, death will be imputed to the maximum of the full (non-imputed) day after the date of last contact and the following:

Missing day: 1st day of the month and year of death, or

Missing day and month: January 1st of the year of death.

Date of Start of New Anti-cancer Therapy

Incomplete dates for new anti-cancer therapy will be imputed as follows and will be used to determine censoring dates for efficacy analyses:

- The end date of new anti-cancer therapy will be included in the imputation for start date of new anti-cancer therapy. If the end data of new anti-cancer therapy is:
 - Completely missing then it will be ignored in the imputations below,
 - Partially missing with only year available then the imputations below will consider 31DECYYYY as the end date of the new anti-cancer therapy, or
 - Partially missing with only month and year available then the imputations below will consider the last day of the month for MMMYYYY as the end date of the new anti-cancer therapy.
- For patients who have not discontinued study treatment at the time of the data cutoff date, last dose of study treatment is set to the data cutoff date in the imputations below.
- If the start date of new anti-cancer therapy is completely or partially missing then the imputed start date of new anti-cancer therapy is:
 - = 31DECYYYY, if only Year is available and Year < Year of min [max (PD date + 1, last dose of study treatment + 1), end date of new anti-cancer therapy]
 - = Last day of the month, if both Year and Month are available and
 - Year = Year of min [max (PD date + 1, last dose of study treatment + 1), end date of new anti-cancer therapy]
 - Month < Month of min [max (PD date + 1 day, last dose of study treatment + 1 day), end date of new anti-cancer therapy]
 - = min [max (PD date + 1, last dose of study treatment + 1), end date of new anti-cancer therapy], for all other cases.

AE Onset Date:

The following imputation rules apply if the event is unique for a patient or it is the first of a series of similar events; otherwise, the AE Onset Date will not be imputed:

- If the AE Collection Date is not missing, is less than the Date of First Exposure to Treatment, and is less than the AE Stop Date, then AE Onset Date is set to the Date of AE Collection.
- If the Previous Visit Date is greater than the Date of First Exposure to Treatment and less than the AE Stop Date, the AE Start Date is set to the previous visit date.

- If the Date of First Exposure to Treatment is greater than the previous visit date and less than the AE Stop Date, the AE Onset Date is set to the Date of First Exposure to Treatment.
- Otherwise AE Onset date is set to the AE Stop date.

AE Stop Date:

Ongoing events will have the AE Stop Date set to one of the following values:

- Date of Death, if the patient died and a date of death exists.
- Maximum of (Patient Withdraw date, AE Onset Date, AE Collection Date) if the patient withdrew from the study and a date of withdraw exists.
- Maximum of (AE Onset Date, Subject Summary Collection Date, AE Collection Date) if the Disposition CRF page exists but a date of withdraw does not exist.
- Maximum of (Last Treatment Date, AE Onset Date) if no Disposition page exists.

Imputation will only occur if event is unique for the patient, or it is the last of a series of similar events; otherwise the Stop Date will not be imputed. Adverse Events are deemed similar if they have the same verbatim term.

Resolved events will have the AE Stop Date set to the maximum of the AE collection date and the AE Onset date.

Other Missing or Partial Dates

Imputation methods for other partial dates as follows:

- If the day of the month is missing for a start date used in a calculation, the first day of the month will be used to replace the missing date.
- If both the day and month are missing, the first day of the year is used.
- For stop dates, the last day of the month, or last day of the year is used if the day or day and month are missing, respectively.
- If the date is completely missing, no imputation will be performed.

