6. ANALYSES AND SUMMARIES

All efficacy analyses will be performed by Cohort on the SA set.

Radiographic images and clinical information collected on study will be reviewed by an ICR. ICR assessment will be used for the primary analysis of OR and for all secondary endpoints based on radiological assessments of tumor burden (ie, IC-OR, DoR, IC-DoR, TTR and PFS). These endpoints will also be derived using the local radiologist's/investigator's assessment.

6.1. Primary Endpoint(s): Objective Response in Cohort 1

The primary efficacy analysis will evaluate the anti-tumor effect of lorlatinib as a single agent as measured by OR per RECIST v1.1 in locally advanced or metastatic ALK-positive NSCLC patients whose disease has progressed after crizotinib treatment.

OR is defined as a complete response (CR) or partial response (PR) recorded from enrollment until disease progression or start of new anti-cancer therapy. Both CR and PR must be confirmed by repeat assessments performed no less than 4 weeks after the criteria for response are first met.

Objective Response Rate (ORR) is defined as the percentage of patients with a best overall confirmed response of CR or PR according to RECIST v1.1 relative to the total patients in the analysis population. Patients without documented CR or PR will be considered as non-responders. Additionally, patients with inadequate data for tumor assessment (eg, no baseline assessment or no follow-up assessments) will be considered as non-responders. The primary evaluation of ORR will be based on ICR's review relative to the SA set.

The exact test will be performed to test the null hypothesis $H_0: ORR \leq 30\%$. One-sided p-value will be provided together with the estimate of ORR and the corresponding exact 95% CI.

Best overall response (BOR) will be assessed based on reported overall responses at different evaluation timepoints by the independent radiologist and by the investigator from the date of first dose until documented disease progression or start of new anti-cancer therapy, according to the following rules:

- CR = at least two determinations of CR at least 4 weeks apart and documented before progression and start of new anti-cancer therapy.
- PR = at least two determinations of PR or better (and not qualifying for a CR) at least 4 weeks apart and before progression and start of new anti-cancer.

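### SAP 5.3.1 has no branch for a partial date with a known month in an earlier calendar year, so a new-therapy start known to precede progression can be imputed to after it

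*SAP*

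**What the plan says.** SAP 5.3.1 states the purpose of the rule: "Incomplete dates for new anti-cancer therapy will be imputed as follows and will be used to determine censoring dates for efficacy analyses". The reference date is min[max(PD + 1, last dose + 1), end date of the new therapy]; a completely missing end date is ignored. Three branches follow:

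1. Year only: "31DECYYYY, if only Year is available and Year < Year of min" of the reference date.
2. Year and month: "Last day of the month, if both Year and Month are available" and two conditions are met. The year must match ("Year = Year of min [max (PD date + 1, last dose of study treatment + 1), end date of new anti-cancer therapy"), and the month must be earlier than the reference month.
3. Every remaining case: the reference date itself.

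The rule for the last dose of study treatment, also in SAP 5.3.1, has the same structure with min(EOT date, death date) as reference. Its month branch applies "if both Year and Month are available and Year = Year of min (EOT date, death date") and the month is earlier.

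The imputed start date is used in two places. SAP 6.2.6 censors PFS at the last adequate assessment before new therapy when that therapy precedes the event. SAP 6.1 counts a response only if "recorded from enrollment until disease progression or start of new anti-cancer therapy", and ends the waterfall and spider plots on the same basis.

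**The concern.** Branch 2 tests for equality of years, so it works only within one calendar year. A record of November 2019 against a reference date in January 2020 fails branch 1, because the month is known, and branch 2, because the years differ. Branch 3 then replaces a month that the site did record with the day after progression or last dose.

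The order of new therapy and progression decides whether a patient is censored or counted as an event in PFS. Reversing it changes that status and leaves the assessment window open past the switch of treatment.

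The situation can arise. Protocol 7.1 continues scans until progression by central review whatever anti-cancer treatment follows, so progression after new therapy is foreseen. Subsequent treatment is collected at survival follow-up, where telephone contact is allowed (Schedule of Activities, footnote 28), so a missing day is plausible.

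**Working it through.** The plan gives no figure to reproduce. The check applies the three branches as written to test dates, then repeats it with year and month compared jointly. The dates are illustrative. The PFS column assumes that no two consecutive assessments were missed, so the 98-day rule does not intervene.

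**Step 1: the failing case.** Recorded start NOV2019 (day unknown), last dose 20OCT2019, PD 15JAN2020, end date missing.
- Reference = max(16JAN2020, 21OCT2019) = 16JAN2020.
- Branch 1 needs the year only, but the month is known: fails.
- Branch 2 needs 2019 = 2020: fails.
- Branch 3 gives 16JAN2020, one day after PD.
- The latest day the record allows is 30NOV2019. The imputed date is 30 days (to 30DEC) + 17 days (to 16JAN) = 47 days later.

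**Step 2: variants and controls.**

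| Recorded start | Last dose | PD | End of new therapy | Rule as written | PFS | Joint comparison | PFS |
|---|---|---|---|---|---|---|---|
| NOV2019 | 20OCT2019 | 15JAN2020 | missing | 16JAN2020 | event | 30NOV2019 | censored |
| NOV2019 | 20OCT2019 | 15JAN2020 | 01MAR2020 | 16JAN2020 | event | 30NOV2019 | censored |
| 2019 only | 20OCT2019 | 15JAN2020 | missing | 31DEC2019 | censored | 31DEC2019 | censored |
| MAR2020 (same year) | 20FEB2020 | 15MAY2020 | missing | 31MAR2020 | censored | 31MAR2020 | censored |
| MAR2019 | 20FEB2019 | 15JUN2020 | missing | 16JUN2020 | event | 31MAR2019 | censored |
| NOV2019 | 20OCT2019 | 15FEB2020 | 10JAN2020 | 10JAN2020 | censored | 30NOV2019 | censored |
| OCT2019 | 20SEP2019 | 15FEB2020 | 10DEC2019 | 31OCT2019 | censored | 31OCT2019 | censored |

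Rows 1 and 3 differ only in whether the month was recorded, and the better-documented start gets the worse date. No conservative convention would produce that. Rows 6 and 7 set the limit. With an end date before PD, the start is at most too late (row 6: 31 + 10 = 41 days) and still precedes PD. If that end date is in the start year, branch 2 can work normally.

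**Step 3: how often a year end intervenes.** Assume start dates uniform over the 365 days of 2019, day unknown, end date missing, and PD a fixed g days after start. The denominator is the starts whose recorded month precedes the PD month. The start goes wrong when PD + 1 falls in the next year.

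| Gap g from start to PD | Imputed after PD | Share |
|---|---|---|
| 30 days | 30/358 | 8% |
| 42 days | 43/365 | 12% |
| 84 days | 85/365 | 23% |
| 126 days | 127/365 | 35% |
| 183 days | 184/365 | 50% |

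With the joint comparison the count is 0 in every row. These shares are conditional on a partial start date and on new therapy before PD. They are not shares of the trial population.

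**Step 4: last dose.** Take a last dose recorded as DEC2019 and an EOT date of 15JAN2020. The years differ, so the rule gives 15JAN2020 instead of 31DEC2019, 15 days later. In SAP 6.4.3.1 treatment duration is then too long, and dose intensity, which divides by duration, too low.

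**The case against.** **Another reading or rule might close the gap.** If the two conditions of branch 2 were alternatives, the MAR2019 case would be repaired. The NOV2019 case would not, because 2019 is not 2020 and November does not precede January. The last-dose rule joins the same conditions with an explicit conjunction. The general partial-date rule at the end of SAP 5.3.1 is headed as covering other dates, so it does not govern dates with their own rule.

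**The conditions are narrow.** This stands. Four things must coincide: a missing day, new therapy before PD, a year end between the two, and an end date that is missing or after PD. A reader might infer that every start in an earlier year is moved past progression; rows 6 and 7 show otherwise. Without PD (taking an absent PD date as ignored), the reference is last dose + 1, and the gap opens only if the last dose falls in a later year than the new therapy. For anti-cancer drugs that is an overlap prohibited by Protocol 5.9.2 and 5.9.3, which is why the example has lorlatinib stopped first.

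**The primary test.** A reader might infer that the gap could decide it, because the exact one-sided p-value at a null of 30% is 0.0386 for 27 of 66 and 0.0216 for 28 of 66. Those figures are correct but describe any single misclassified patient at the cut-off. A false responder from this cause would also need no response confirmed before the switch, and a qualifying CR or PR after it, before PD and at least 4 weeks from the other determination. Scans are every 6 weeks, so the 46 days from 30NOV2019 to 15JAN2020 hold about one. The documents give no basis for expecting this.

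**PFS is secondary and descriptive.** This also stands. Counting a censored time as an event does not clearly favour lorlatinib.

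**Last dose.** Errors of many months do not follow. The fallback is the EOT or death date, and the EOT visit is due within 4 weeks (+1 week) of the last dose (Protocol section 7). If the EOT date means that visit and it is on time, the overstatement is at most about 5 weeks.

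**Conclusion.** The gap is real and follows from the SAP text alone: a known month in an earlier year has no branch and is replaced by the reference date. When the new therapy's end date is missing or later than PD, a start known to precede PD is placed after it. The error is 47 days in the main example. In the MAR2019 example it is 443 days (366 from 31MAR2019 to 31MAR2020, plus 77 to 16JUN2020).

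For such a patient, PFS is an event instead of a censored time, and scans after the switch may enter best overall response and the tumour-change plots. The last-dose version affects descriptive exposure summaries and is bounded by the EOT or death date.

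Few patients are likely affected. The number cannot be derived from the documents, and the shares in step 3 rest on assumed uniform starts and fixed gaps. This is a drafting error worth correcting because the date is wrong and the repair is simple. It is not evidence that the primary conclusion is at risk.

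**What to change.** In SAP 5.3.1, in both the rule for the start of new anti-cancer therapy and the rule for the last dose, replace the month-known condition with: Year < reference year, OR (Year = reference year AND Month < reference month). Impute the last day of the recorded month in either case. Same-year and year-only records keep their present result.

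The cost is one condition in two SAP bullets and the matching program lines. No new data and no protocol change are needed. SAP 5.3.1 already compares month and year together when it decides whether a partial adverse event or medication date precedes first dose, so the change follows a convention the plan uses.

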8.1.4. Time Period for Collecting AE/SAE Information

The time period for actively eliciting and collecting AEs and SAEs (“active collection period”) for each subject begins from the time the subject provides informed consent, which is obtained before the subject’s participation in the study (ie, before undergoing any study-related procedure and/or receiving investigational product), through and including a minimum of 28 calendar days after the last administration of the investigational product.

For subjects who are screen failures, the active collection period ends when screen failure status is determined.

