3.5. Safety Endpoints

Safety endpoints will be summarized based on the on-treatment period unless otherwise specified.

On-treatment is defined as the time from the first dose of study treatment through the end of study follow-up (infinite lag) or start of new anti-cancer drug therapy, whichever occurs first. Adverse events occurring on the same day as the first dose of study treatment will be considered to have occurred during the on-treatment period. All other assessments which occur on the same day as the first dose of study treatment will be considered baseline assessments (see [Section 3.4](#) for the definition of baseline).

Safety data collected outside the on-treatment period as described above will be listed but not summarized.

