5.2.5. Definition of Start of New Anti-cancer Drug Therapy

Start date of new anti-cancer drug therapy is used to determine the end of the on-treatment period (see [Section 3.5](#)).

The start date of new anti-cancer drug therapy is the earliest start date of anti-cancer drug therapy recorded in the 'Follow-up Cancer Therapy' eCRF pages that is after the first dose of study treatment. When start date of anti-cancer drug therapy is missing or partially missing, the imputation rules described in [Section 5.3.4](#) should be applied using only data from the 'Follow-up Cancer Therapy' eCRF pages.

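### SAP 5.3.1 can impute the start of a new anti-cancer therapy outside the recorded month or year; the efficacy effect falls mainly on patients who stop without progression

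*SAP*

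**What the plan says.** SAP 5.3.1 (Date of Start of New Anti-cancer Therapy) builds a reference date R: the earlier of the therapy's end date and the later of PD + 1 and last dose + 1. It then has three branches:

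- Year only, and earlier than the year of R: 31 December of that year.
- Year and month known, same year as R, and "Month < Month of min [max (PD date + 1 day, last dose of study treatment + 1 day" and so on: last day of the known month.
- Everything else: "min [max (PD date + 1, last dose of study treatment + 1), end date of new anti-cancer therapy], for all other cases".

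The section says that these dates "will be used to determine censoring dates for efficacy analyses", and SAP 5.2.6 refers to it for that purpose. SAP 6.1 requires the two determinations of CR to be "at least 4 weeks apart and documented before progression and start of new anti-cancer therapy", with a parallel rule for PR. SAP 6.2.6 censors PFS at the last adequate scan before new therapy.

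On the safety side, SAP 3.5 ends the on-treatment period at "end of study follow-up (infinite lag) or start of new anti-cancer drug therapy, whichever occurs first", and "Safety data collected outside the on-treatment period as described above will be listed but not summarized". SAP 5.2.5 confirms that "Start date of new anti-cancer drug therapy is used to determine the end of the on-treatment period", but for incomplete dates it points to Section 5.3.4, which is Missing ECG Data. Protocol 8.1.4 collects adverse events for "a minimum of 28 calendar days after the last administration of the investigational product". Under Protocol 7.1, patients who stop without progression are scanned every 6 weeks until central review documents it, whatever treatment follows.

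**The concern.** The two specific branches use the recorded period only when it is earlier than R. A later month or year has no branch, and neither does a month-and-year date in an earlier year. Both are overwritten by R, so the imputed date contradicts what the site recorded.

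The same three-branch layout is used for the last-dose date in SAP 5.3.1. It is safer there, because the earlier of end of treatment and death is an upper limit for last dose. R is not an upper limit for the start of new therapy. Protocol 5.9.2 bars concurrent anti-tumour treatment, so new therapy normally starts after last dose. Other rules in SAP 5.3.1 do respect a known month: a partial death date is never placed before the first of its recorded month, and other start dates missing only the day go to the first of the month.

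At stake are the confirmation of some responses, the PFS censoring date in patients without progression and, on one reading of SAP 5.2.5, safety data collected after the last dose.

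**Working it through.** **1. The plan's own figure.** Cohort 1 rejects ORR ≤ 30% with at least 28 of 66 responses (SAP 5.1.2). Exact binomial: P(X ≥ 28 | n = 66, p = 0.30) = 0.0216, below 0.025. Power is P(X ≥ 28 | n = 66, p = 0.50) = 0.912, against the stated 90%. The design reproduces.

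**2. The rule applied literally.** The dates are illustrative and the therapy end date is missing. A missing PD date is ignored in the maximum; the SAP does not say how to treat it.

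| PD | Last dose | Therapy recorded | R | Imputed start | Against recorded period |
|---|---|---|---|---|---|
| none | 10 Feb 2020 | Jul 2020 | 11 Feb 2020 | 11 Feb 2020 | before |
| 10 Feb 2020 | 20 Feb 2020 | Mar 2020 | 21 Feb 2020 | 21 Feb 2020 | before |
| none | 20 Oct 2019 | 2020 | 21 Oct 2019 | 21 Oct 2019 | before |
| none | 10 Jan 2020 | Nov 2019 | 11 Jan 2020 | 11 Jan 2020 | after |
| none | 10 Jan 2020 | Jan 2020 | 11 Jan 2020 | 11 Jan 2020 | inside |
| 20 Apr 2020 | 10 Jan 2020 | Mar 2020 | 21 Apr 2020 | 31 Mar 2020 | inside |

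A known end date does not repair the first type of case. It cannot precede the therapy's own month, so the minimum still picks the earlier date. With last dose 10 Jan 2020, no PD and therapy in March 2020, end dates of 31 Mar or 15 Jun both still give 11 Jan 2020.

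**3. Efficacy, no PD.** Take row 1, with PR on 3 Feb and 16 Mar 2020 and scans without progression to 8 Jun.

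- As written: start = 11 Feb. The 16 Mar scan falls after it, so the PR is unconfirmed and the patient is a non-responder. PFS is censored at 3 Feb.
- Keeping the recorded month: start = 1 Jul. The two PRs are 42 days apart (at least 28 needed), so the response is confirmed. PFS is censored at 8 Jun.
- Difference in PFS follow-up: 3 Feb to 8 Jun = 126 days; 126 / 30.4375 = 4.1 months.

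**4. Efficacy, with PD.** R is at least PD + 1 unless the therapy's end date is earlier. When PD is on or before R, the PFS event normally stands, and responses after PD would not count anyway. Row 2 therefore has no efficacy effect.

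**5. Safety, if 5.3.1 is the intended rule.** The minimum backdating is the first of the recorded month minus R. Over every last-dose day in a year, without PD:

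| Therapy month relative to last dose | Range (days) | Mean (days) |
|---|---|---|
| next calendar month | 0–30 | 15 |
| two months later | 28–61 | 45 |
| three months later | 59–91 | 76 |

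In row 2 it is 9 days (21 Feb to 1 Mar 2020). The whole 28-day window is lost only when therapy starts about a month or more after last dose.

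**6. Primary endpoint.** One response is 1/66 = 1.5 percentage points. 28/66 gives p = 0.0216 (reject); 27/66 gives P(X ≥ 27 | p = 0.30) = 0.0386 (do not reject).

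**The case against.** The case for treating this as minor is strong in several respects.

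- **Frequency.** The protocol collects administration dates of subsequent therapy, and nothing says how often they will be incomplete. Collection every 4 months, by telephone if needed (Schedule of Activities, footnote 28), makes partial dates plausible but gives no rate. This stands.
- **Joint conditions.** Losing a responder requires stopping without PD, between first response and confirmation, with an incomplete therapy date in a later month. In the earlier study 7.8% discontinued permanently for an adverse event (Protocol 1.2.3.4), or about 0.078 × 66 = 5 patients before the other conditions apply. That is only indicative, since toxicity is not the only reason to stop without PD.
- **Boundary.** With one lost response, the decision changes only if exactly 28 would otherwise have been counted. At a true ORR of 50%, where 33 are expected, P(X = 27) = 0.9456 − 0.9124 = 0.0332 and P(X = 28) = 0.0332 × 39/28 = 0.046.
- **Direction.** Backdating can only remove responders, so it cannot favour lorlatinib on ORR. This holds for dates later than R. The earlier-year gap moves the date forward and can work the other way, keeping scans taken after the true start.
- **Safety.** Read literally, SAP 5.2.5 does not invoke this rule, and the default for other start dates in 5.3.1 would give the first of the month. Section 5.3.1 is nevertheless the probable target: the parallel SAP 5.2.6 cites it, and 5.3.4 contains no such rule. Deaths are tabulated separately (SAP 6.5.2), recording of non-serious events ends at the true start of new therapy anyway (Protocol 8.1.4.2), and excluded data remain in listings.

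A reader might infer that patients with progression also lose PFS events, that 28 days of safety data are always lost, or that the primary conclusion is in jeopardy. The documents support none of these: R normally follows PD, the safety loss varies with the gap, and no frequency is given.

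**Conclusion.** The rule is wrong as written. It produces a start date that contradicts the recorded month or year whenever that period is later than R, and also for a month-and-year date in a year before R. For dates later than R, the loss of response confirmation and of PFS follow-up arises essentially in patients who stop without PD. The 126 days is one constructed case and not an expected value. The safety effect is conditional on 5.3.1 being the section intended in SAP 5.2.5; its size runs from a mean of about 15 days, when therapy starts in the next calendar month, to the full 28-day window when it starts later.

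The total effect on the trial cannot be estimated from the documents. Each lost Cohort 1 response costs 1.5 points of ORR, and a changed decision arises only at the boundary. The worked dates assume that a missing PD date is ignored in the maximum. The case for changing the rule is that the error is certain in logic and cheap to remove.

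**What to change.** Rewrite the rule in SAP 5.3.1 so that the imputed date stays inside the recorded period:

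- If the known year, or year and month, is later than that of R, use the first day of that period.
- If it is earlier, including a month-and-year date in an earlier year, use the last day of that period.
- Otherwise use R.

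In the examples, July 2020 becomes 1 Jul 2020, March 2020 in row 2 becomes 1 Mar 2020, and November 2019 becomes 30 Nov 2019. State in the same place how a missing PD date enters the maximum. Change the cross-reference in SAP 5.2.5 from 5.3.4 to 5.3.1.

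The cost is one revised SAP rule, one corrected reference and one programming condition. No new data are needed.
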